Phase IA/IB Trial of Real-time MRI-Guided Stereotactic Body Radiation Therapy and Microwave Ablation for Non-Operable Renal Cell Carcinoma

NCT02782715

PI:

[name] MD PhD
Assistant Professor
Department of Human Oncology
University of Wisconsin Hospital and Clinics
[name]
[name]

[contact]

[contact] [name]

[contact] [name]

Co-Investigators:

[name] MD
Assistant Professor
Department of Urology
University of Wisconsin Hospital and Clinics
[name]
[name]

[name] MD
Assistant Professor
Department of Urology
University of Wisconsin Hospital and Clinics
[name]
[name]

[name] PhD
Professor
Department of Biostatistics & Medical Informatics and Department of Statistics
University of Wisconsin Hospital and Clinics
[name]
[name]

[name] MD
Professor
Departments of Radiology and Biomedical Engineering
University of Wisconsin Hospital and Clinics
[name]
[name]

[name] MD
Associate Professor
Department of Radiology
University of Wisconsin Hospital and Clinics
[name]
[name]

Study Center: University of Wisconsin Hospital and Clinics

SYNOPSIS:

Title	Real-time MRI-Guided Stereotactic Body Radiation Therapy and Microwave Ablation for Non-Operable Renal Cell Carcinoma
Short Title	Microwave ablation with MRI-Guided SBRT Boost in Renal Cell Carcinoma
Protocol Number/ Date	UW15103
Study Duration	5 years
Study Center(s)	University of Wisconsin Hospital and Clinics Carbone Cancer Center, Madison, WI
Objectives	
Primary Objective(s): The primary objective of this study is to determine the maximum tolerated dose (MTD) of stereotactic body radiation therapy followed by microwave ablation for non-operable renal cell carcinoma.
 
Secondary Objective(s): The secondary objectives of this study include estimation of rates of local control, progression-free survival, overall survival, and tumor response on biopsy.

Number of Subjects	Based on the 3+3 dose-escalation design, between 9-18 patients will be enrolled in the initial Phase IA study, with an optional 10 patients enrolled on a Phase IB expansion cohort.
Inclusion Criteria	
 1. Histologically confirmed diagnosis of renal cell carcinoma 2. Tumor size >4cm in largest dimension 3. ECOG performance status of < 2 4. Age > 18 years 5. Signed informed consent document(s) 6. Patients with metastatic disease will not be excluded
Treatment summary	
The proposed study would be performed as a 3+3 dose-escalation study wherein three dose levels of SBRT would be evaluated:
 
 1. Dose level I: 6 Gy x 5 fractions 2. Dose level II: 8 Gy x 5 fractions 3. Dose level III: 10 Gy x 5 fractions 
Radiation treatments will be delivered two to three times a week, with five fractions completed over two weeks.
 
Four to six weeks after radiation treatment, patients will undergo repeat CT or MRI imaging to assess tumor response and suitability for microwave ablation.
 
Eight weeks after the conclusion of SBRT, patients will undergo microwave ablation (approximately 12 weeks after registration).

SCHEMA

Phase I: Microwave ablation with MRI-Guided SBRT Boost in Renal Cell Carcinoma

Informed Consent

Registration in study, if eligibility criteria satisfied

SBRT (week 1 and 2)

Dose-escalation levels (for Phase IA):

- Dose level I: 6 Gy x 5 fractions
- Dose level II: 8 Gy x 5 fractions
- Dose level III: 10 Gy x 5 fractions

Dose-level for Phase IB will be based on the MTD from Phase IA

Four weeks after SBRT completion: Assessment for ablation

Microwave ablation 8 weeks
from the completion of SBRT

Table of Contents

- 1.0 Protocol Summary
- 2.0 Introduction
- 3.0 Study Objectives
- 4.0 Selection of Patients
 - 4.1 Inclusion
 - 4.2 Exclusion
- 5.0 Registration Procedures
- 6.0 Treatment Plan
 - 6.1 Overview
 - 6.2 Dose Escalation
 - 6.3 Pretreatment Workup
 - 6.4 Radiotherapy
 - 6.5 Microwave Ablation
 - 6.6 Pathology
 - 6.7 Other Therapy
 - 6.8 Duration of Therapy
 - 6.9 Follow-up
 - 6.10 Criteria for Removal from Treatment
- 7.0 Measurement of Treatment
 - 7.1 Toxicity Assessment
 - 7.2 Local Control
- 8.0 Study Parameters
- 9.0 Statistical Analysis
 - 9.1 Number of Patients
 - 9.2 Study Endpoints
 - 9.3 Definition of endpoints
 - 9.4 Statistical Analysis
 - 9.5 Justification of Future Studies
- 10.0 Pathology Review
- 11.0 Data Collection
- 12.0 Patient Consent
- 13.0 Safety Monitoring
 - 13.1 SBRT
 - 13.2 Microwave Ablation
 - 13.3 Adverse Event Characteristics
 - 13.4 Adverse Event Reporting
 - 13.5 Stopping Rules
- References

- Appendix 1: Eligibility Checklist
- Appendix 2: UWCCC Data Safety Monitoring plan

1. Protocol Summary

Renal cell carcinoma is traditionally managed via a surgical approach. Increasingly, local therapy with radiofrequency and microwave ablation is being utilized as an alternative for patients who may not tolerate a nephrectomy or who refuse one. Although local control rates for small lesions are excellent, they drop off precipitously for lesions over 4 cm. Furthermore, lesions in critical areas such as the renal hilum may be difficult to treat with this method. Stereotactic body radiation therapy (SBRT) has had a long record of treating patients with inoperable tumors in locations such as the lung and central nervous system, and there is increasing evidence that it may be useful for patients with renal cell carcinoma. The recent emergence of MRI-guided radiation therapy allows for direct visualization of tumors during treatment, and may potentially allow clinicians to treat tumors more precisely. This phase I study will treat renal cell carcinoma patients using a combination of MRI-guided stereotactic body radiation therapy and microwave ablation.

The specific aims of this study are:

1. To determine the safety and feasibility of treating patients with a combination of MRI-guided stereotactic body radiation therapy and microwave ablation.
2. To assess short and long-term toxicity rates of patients treated with a combined modality approach.
3. To assess local control, survival, and pathologic response to treatment

2. Introduction

The traditional management of renal cell carcinoma (RCC) has been total or partial nephrectomy. This has been shown to prevent long-term renal failure and cardiovascular disease, as well as decrease overall mortality[1]. Cytoreductive treatment has even been found to improve overall survival in the metastatic setting[2,3]. With the increasing numbers of renal masses found incidentally on routine imaging, focal therapies are being increasingly utilized as an alternative to partial nephrectomy for carefully selected patients who might not tolerate a nephrectomy or who refuse one. Studies of radiofrequency ablative treatments have reported disease-free survival, overall survival, and cause-specific survival rates of 83.1-97%, 63-97.8%, and 96.4-100%, respectively[4]. More recently, microwave ablation has emerged as an alternative to radiofrequency ablation with promising early results[5,6]. Although thermal ablative strategies may be comparable to partial nephrectomy especially when balanced against the potential morbidity of surgery, they are less effective at controlling larger tumors. Three centimeters has emerged as a common threshold above which thermal ablative strategies are less commonly recommended, with 5-year disease-free survival decreasing from 96% to 79%[7]. Microwave ablation is effective to 4cm; as with RFA, however, local control rates drop precipitously for tumors above 4cm[8].

The role of external beam radiation therapy in the treatment of RCC is less established, as it is typically considered a radioresistant entity. Radiation therapy is usually given in 30 or more doses of 2 Gy per fraction, delivered daily over several weeks. Stereotactic body radiation therapy (SBRT) differs from conventionally fractionated treatment, using radiation doses of up to 34 Gy in a single fraction. It is believed that at such high doses, radiation therapy is ablative[9]. Advances in physics, imaging, and motion management have made such treatment possible and it is considered standard of care in

medically inoperable non-small cell lung cancer [10]. Phase I studies utilizing SBRT in the treatment of renal cell carcinoma show promising results[11,12].

One challenge that exists when utilizing high doses of radiation therapy in the kidney is that of respiratory induced tumor motion. Respiratory gating techniques are utilized to minimize normal tissue irradiation. Nevertheless, any such technique is limited by the fact that it depends on the assumption that there is a good correlation between respiratory motion and tumor motion.

The recent emergence of a radiation treatment system allowing real-time MRI imaging during treatment may obviate the dependence on respiratory gating techniques[13]. Tracking tumor motion in real time allows the potential for the delivery of safe and effective radiation treatment with the goal of improving control rates of ablative treatments for large, medically inoperable renal cell carcinomas.

We propose a Phase I study to determine the feasibility of adding SBRT treatment for patients undergoing treatment for RCC. We hope to show that such treatment is feasible and safe.

3. Study Objectives

- 3.1 Working hypothesis – We hypothesize that the addition of SBRT treatment to microwave ablation is safe and can be delivered without undue toxicity.
- 3.2 Primary Objective - The primary objective of this study is to determine the maximum tolerated dose (MTD) of stereotactic body radiation therapy followed by microwave ablation for non-operable renal cell carcinoma. Toxicity will be evaluated via the CTCAE Criteria v5.0. Expected side effects of radiation treatment include potential fatigue, dermatitis, chest wall pain, nausea, and hematuria. Side effects of ablation may include hemorrhage, treatment site pain, urinary retention, and a decrease in glomerular filtration rate.
- 3.3 Secondary Objective - The secondary objectives of this study include estimation of rates of local control, progression-free survival, overall survival, and tumor response on biopsy.
- 3.4 Exploratory Objective – To assess pathologic response after stereotactic body radiation therapy and immune cell infiltrate.
- 3.5 Study Duration – We estimate that approximately 40-50 potentially eligible patients are seen at UWCCC each year. With a 3+3 study design and an estimated 20% rate of enrollment, we estimate it will take 1-2 years for patient accrual, treatment, and followup for determination of acute toxicity of the initial 9-18 patient Phase IA cohort. This cohort will then be followed for a period of 3 years, giving an estimated study duration of 5 years.

4. Selection of Patients

- 4.1 Inclusion Criteria
 - 4.1.1 Patients with imaging findings consistent with renal cell carcinoma
 - 4.1.2 Deemed medically inoperable per urology evaluation
 - 4.1.3 Tumor size > 4cm in largest dimension

- 4.1.4 ECOG performance status of < 2
- 4.1.5 Age > 18 years
- 4.1.6 Signed informed consent document(s)
- 4.1.7 Patients with metastatic disease will not be excluded

4.2 Exclusion Criteria

- 4.2.1 Patients who fail MRI screening
- 4.2.2 Pregnant or nursing women
- 4.2.3 History of prior radiation therapy to the upper abdomen
- 4.2.4 History of invasive cancer in the last 3 years (except for appropriately treated low-risk prostate cancer, treated non-melanoma/melanoma skin cancer, appropriately treated ductal carcinoma in situ or early stage invasive carcinoma of breast and appropriately treated in-situ/early stage cervical/endometrial cancer)
- 4.2.5 Treatment with a non-approved or investigational drug within 28 days of study treatment

5. Registration Procedures

Patients may not begin protocol treatment prior to registration. All patients must meet eligibility criteria listed in Section 4 and provide written informed consent. The study coordinator will verify eligibility, assign a case number, and register the patient in the UWCCC ONCORE database prior to study treatment. The following information will be recorded:

- 5.1 Protocol number
- 5.2 Patient's name and initials
- 5.3 Patient's medical record number
- 5.4 Patient demographic data including gender, birth date, race and zip code.
- 5.5 Signed patient consent form dates
- 5.6 Attending physician
- 5.7 HIPAA authorization form dates

[figure not shown]
6. Treatment Plan/Overview

6.1 Overview

Patients will be referred to the study by their treating urologist. The urologist will determine the appropriateness for patient referral and discuss the option of study participation with their patients. After biopsy, patients will be treated on study with a course of SBRT treatment by a radiation oncologist. A 3+3 dose escalation scheme will be used. Four to six weeks after treatment, patients will be evaluated for microwave ablation by the treating radiologist with repeat imaging to ensure microwave ablation remains feasible. Two months after treatment, patients will be referred to an interventional radiologist for treatment with microwave ablation as well as repeat biopsy for exploratory analysis. Both SBRT and MWA will be administered on an outpatient basis. Details of treatment are as described below.

6.2 Dose escalation

- 6.2.1. The proposed study will follow a phase IA-B dose-escalation design wherein three SBRT dose levels targeting the primary tumor will be evaluated; level I: 6 Gy x 5 fractions (a common palliative dose), level II: 8 Gy x 5 fractions and level III: 10 Gy x 5 fractions (a common definitive dose).
- 6.2.2. Dose-limiting toxicity (DLT) will be defined as any grade 4 or higher toxicity that occurs within 30 days post MWA (approximately 90 days post SBRT) specifically: hemorrhage, hematoma, nephrotoxicity, gastric, duodenal or small bowel perforation or obstruction attributable to the radiation, the MWA or the combination of the treatment. Attributable DLT will be defined as that which is possibly, probably or definitely felt to be due to either radiation or ablation and occurring within the vicinity of the radiation treatment field (as reviewed by Drs. [name]/[name]) or in the vicinity of the microwave ablation (as reviewed by [name]). Grade 3 toxicity is not considered a DLT as it may be seen in routine, standard of care treatment. If progressive disease is found at the time of interval imaging and the patient is deemed ineligible for MWA, the patient will not be part of the cohort used for DLT analysis as his/her inclusion may falsely lower potential toxicity rates.
- 6.2.3. A standard, traditional 3+3 design will be utilized for dose escalation (Figure). For each three patient cohort, DLT will be assessed. In the case of 0/3 DLTs, the dose will be escalated to the next level. In the case of 2/3 DLTs, the dose escalation will be halted with the previous level being the MTD. In the case of 1/3 DLTs, an additional three patients will be enrolled at the current dose level. If no additional DLTs are seen, the dose will be escalated to the next level. In the event of a total of 2 or more DLTs in 6 patients, the dose escalation will be halted with the previous dose level being the MTD. Once the MTD has been established, the MTD will be used for the subsequent Phase IB expansion cohort.
- 6.2.4. Dose escalation/de-escalation will continue until a maximum of 18 patients are accrued or dose-level I is shown to exceed the MTD. To allow efficient conduct of the study without compromising patient safety, accrual in the phase-IA study will be done in groups of three patients, with subsequent dose level accrual only after the occurrence of DLT thirty days after ablation has been evaluated for all at the current dose level. The phase-IB portion of the trial will consist of an additional ten patients (for a theoretical maximum of 28 total patients) to validate the results of phase-IA and provide a preliminary assessment of efficacy.

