7.1 Toxicity Assessment

- 7.1.1. Dose-limiting toxicity (DLT) will be defined as grade 4 non-hematologic/grade 5 toxicity attributable to treatment, occurring until 30 days after ablation. Patients will be monitored and assessed for unexpected long-term toxicity during the post-treatment followup period. In the case of unexpected long-term toxicity, the dose level will be evaluated and potentially used to recalculate the MTD. Potential toxicities due to stereotactic body radiation therapy and microwave ablation are listed in Section 13.1 and 13.2 respectively. The most likely acute side effects of treatment include fatigue, nausea, vomiting, and pain due to the procedure. Toxicities not caused by treatment, such as pain due to tumor progression, will be excluded from the assessment.

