9.3 Definition of end-points

- 9.3.1 Primary Endpoint of the Phase I study:

Dose-limiting toxicity (DLT) will be defined as grade 4 or higher non-hematologic toxicity attributable to treatment occurring until 30 days after ablation. This will exclude toxicities not caused by treatment, such as pain due to tumor progression. Toxicities will be defined per NCI CTCAE v5.0.

- 9.3.2 Secondary endpoints of the Phase I study:
 - 9.3.2.1 Local control: Radiologic response per RECIST criteria and volumetric measurements.
 - 9.3.2.2 Progression free survival defined with follow-up radiological assessment with progression free survival (PFS) calculated from the point of start of SBRT to the point of recurrence or death.
 - 9.3.2.3 Overall survival (OS) defined from the point of start of SBRT to the time of death or last follow-up if alive.
 - 9.3.2.4 Tumor pathology: H&E staining and pathologic evaluation for percentage of viable tumor remaining as measured by the presence of necrosis, fibrosis, hyalinization, and/or calcification, compared to pre-SBRT pathology.

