9.4 Statistical Analysis

- 9.4.1 Primary objective of Phase I study:

A 3+3 design will be utilized for dose escalation. For each three patient cohort, DLT will be assessed as above. In the case of 0/3 DLTs, the dose will be escalated to the next level. In the case of 2/3 DLTs, the trial will be terminated with the previous level being the MTD. In the case of 1/3 DLTs, an additional three patients will be enrolled at the current dose level. If no additional DLTs are seen, the dose will be escalated to the next level. In the event of a total of 2 or more DLTs in 6 patients, the trial will be terminated with the previous dose level being the MTD. Toxicities will be tabulated by type and grade.

- 9.4.2 Secondary objectives of Phase I study:

- 9.4.2.1 Local control will be reported actuarially as a percentage with an associated 95% exact confidence interval.
- 9.4.2.2 Progression free and overall survival will be estimated using the Kaplan-Meier method. For calculation of PFS, patients without recurrence and alive at last follow-up will be censored at the date of the last radiologic assessment. For calculation of OS, patients alive at last follow-up will be censored. Log-rank test and Cox regression analysis will be used for univariate and multivariate analyses, respectively. Chi-square and regression analysis will be performed to test association of categorical variables with treatment response.
- 9.4.2.3 Tumor response will be reported via rates of complete response, partial response, and no response.

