13.2 Adverse Event List for Microwave Ablation/Biopsy

Likely

Pain

Paresthesia

Post-ablation syndrome

Nausea

Vomiting

Malaise

Fever

Hematuria

Acute Kidney Injury

Less Likely

Hemorrhage

Hematoma

Rare but serious late effects

Bladder outlet obstruction

Bowel perforation or ulceration

Nephrotoxicity

Myelopathy

Chronic Kidney Injury

Ureteral damage

Tumor seeding

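### Section 6.2.2 confines DLTs to a named event list, Sections 9.3.1 and 7.1.1 have no list, and nothing says which definition drives the 3+3 rule

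*Combined protocol and SAP*

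**What the plan says.** Three sections of the combined protocol and SAP each offer a definition of DLT.

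- **6.2.2 (Dose escalation)** opens with any toxicity of grade 4 or higher up to 30 days after microwave ablation (MWA), then narrows it: "specifically: hemorrhage, hematoma, nephrotoxicity, gastric, duodenal or small bowel perforation or obstruction attributable to the radiation", the MWA, or the two combined. It defines attribution as possible, probable or definite, with the event "occurring within the vicinity of the radiation treatment field" or near the ablation, as judged by named reviewers.
- **7.1.1 (Toxicity Assessment)** has no list: "grade 4 non-hematologic/grade 5 toxicity attributable to treatment, occurring until 30 days after ablation".
- **9.3.1 (primary endpoint)** has no list either: "Dose-limiting toxicity (DLT) will be defined as grade 4 or higher non-hematologic toxicity attributable to treatment occurring until 30 days after ablation".

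The 3+3 rule then appears more than once. In 6.2.3, immediately after the 6.2.2 definition: "For each three patient cohort, DLT will be assessed. In the case of 0/3 DLTs, the dose will be escalated to the next level". In 9.4.1, within the statistical section and after the endpoint definitions of 9.3: "For each three patient cohort, DLT will be assessed as above". Section 13.5.1 restates the rule, also pointing only to what came above. No section refers from one DLT definition to another or ranks them.

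The protocol's own adverse event lists contain items missing from 6.2.2. Section 13.2 has "Bowel perforation or ulceration" (not limited to small bowel), "Ureteral damage" and myelopathy. Section 13.1 has hepatotoxicity.

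**The concern.** DLT is the primary endpoint. It determines the MTD, and the MTD is the Phase IB dose. A 3+3 decision turns on one or two events, so an event that is a DLT in one section and not in another can change the decision by itself.

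Read naturally, the word 'specifically' followed by a colon closes the list. A team working from Section 6.2 could then raise the radiation dose after an attributable grade 4 colonic perforation that Section 9.3.1 counts as a DLT. A closed list can only make the rule more permissive than 9.3.1. If the question first arises when such an event occurs, the choice of definition becomes a choice of primary endpoint made with the data in view.

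**Working it through.** **1. The plan's own figure.** Three levels of 3 or 6 patients give 3 × 3 = 9 and 3 × 6 = 18 in Phase IA, and 18 + 10 = 28 with Phase IB. These match the plan and are the same under either definition.

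**2. The definitions compared.** All three use grade 4 or higher, attribution to treatment, and an end point 30 days after MWA. The substantive difference is the list. The vicinity test appears only in 6.2.2, but as part of what attributable means there, and 7.1.1 and 9.3.1 also require attribution.

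**3. What one off-list event does in a first cohort of three.**

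| Events in three patients | 6.2.2, closed list | 9.3.1 |
|---|---|---|
| None listed, one off-list | 0/3, escalate | 1/3, add three |
| One listed, one off-list in another patient | 1/3, add three | 2/3, stop |

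**4. Probability of escalating from a level.** The documents give no event rates. Assume a per-patient listed rate a of 5%, 10% or 20% and an off-list rate b of 1% or 2%, with 5% as a stress case, the two kinds of event being independent. The DLT probability is a under 6.2.2 and p = 1 − (1 − a)(1 − b) under 9.3.1. Two or more DLTs stop escalation, so with DLT probability p

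P(escalate) = (1 − p)³ + 3p(1 − p)² × (1 − p)³.

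For a = 0.10: 0.729 + 0.243 × 0.729 = 0.906. Adding b = 0.02 gives p = 0.118 and 0.686 + 0.275 × 0.686 = 0.875, a gap of 3.1 points.

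| Listed rate | 6.2.2 | 9.3.1, b = 1% | b = 2% | b = 5% |
|---|---|---|---|---|
| 5% | 0.973 | 0.963 | 0.952 | 0.910 |
| 10% | 0.906 | 0.891 | 0.875 | 0.824 |
| 20% | 0.709 | 0.691 | 0.674 | 0.622 |

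From unrounded values, the gaps are 1.0-1.7 points at b = 1%, 2.2-3.5 at 2% and 6.3-8.7 at 5%.

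**5. Probability that the first-cohort decision differs.** Per patient, let L = a, O = (1 − a)b and N = (1 − a)(1 − b).

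- Escalate versus add three: 3ON²
- Add three versus stop: 3L[(O + N)² − N²]
- Escalate versus stop: 3O²N + O³

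For a = 0.10 and b = 0.02: O = 0.018, N = 0.882, and the terms are 0.0420 + 0.0096 + 0.0009 = 0.0525. Over listed rates of 5-20%, the total is 2.3-2.8% at b = 1%, 4.5-5.6% at 2% and 11.0-13.5% at 5%. Most of it is escalate versus add three.

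**6. Consequence for the whole of Phase IA.** With the same rates at every level and E = P(escalate), the chance of clearing all three levels is E³. Expected patients at a level that is opened are m = 3 + 9p(1 − p)², and expected Phase IA size is m(1 + E + E²). For a = 0.10:

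| | 6.2.2 | 9.3.1, b = 1% | 9.3.1, b = 2% |
|---|---|---|---|
| Clears all three levels | 74.4% | 70.7% | 67.0% |
| Expected Phase IA size | 10.17 | 10.15 | 10.10 |

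The broader definition sends more cohorts to six patients but also stops escalation sooner, so expected size hardly moves.

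**The case against.** The strongest reply is that the sections can be reconciled. Section 6.2.2 begins with any toxicity of grade 4 or higher, and a closed list makes the word 'any' nearly redundant. If the list only names the events of most concern, the three definitions nearly agree. The text permits that reading, so a reader should not infer that the sections conflict on every reading. But 'specifically' more naturally limits than illustrates, and nothing in the document settles it.

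Second, 9.3.1 is labelled as the primary-endpoint definition, 7.1.1 largely matches it, and the reference in 9.4.1 fits it. The statistical section is coherent and 6.2.2 is the outlier. That is a good reason to let 9.3.1 govern, but the rule in 6.2.3 still sits directly under the other definition.

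Third, the off-list examples come from the lists of rare but serious late effects in 13.1 and 13.2, so most fit a window ending 30 days after MWA poorly. Some ureteral injuries might also be classed as nephrotoxicity, which is listed. This stands and keeps the effect small. Early ablation injury to colon or ureter remains possible.

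Fourth, such an event would not go unreviewed. Section 6.2.2 has attribution reviewers, 6.9.3 allows treatment to be withheld for other unacceptable events, 7.1.1 allows unexpected long-term toxicity to revise the MTD, and the disease-oriented working group and the data and safety monitoring committee review toxicity. These are real safeguards, but none of them is told which definition to apply.

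**Conclusion.** The primary endpoint is defined inconsistently, and the wording should be corrected. On the natural reading of 6.2.2, the two statements of the 3+3 rule can give different decisions on the same data.

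The expected effect is small: 1.0-3.5 points in the probability of escalating per level, and a different first-cohort decision 2.3-5.6% of the time. These figures rest on assumed off-list rates of 1-2%, listed rates of 5-20%, independence, and a closed reading of the 6.2.2 list. The case for acting is that the discrepancy lies in the rule that sets the MTD, runs toward escalation, and is cheap to remove.

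Two stronger inferences are not supported. A reader might conclude that the choice of definition transforms the trial: with off-list rates of 10% on top of a 10% listed rate, the chance of clearing three levels falls from 74.4% to 38.9%. Rates of that size do not fit events the protocol calls rare, and even 5% is only a stress case. A reader might also treat the absence of 'non-hematologic' from 6.2.2, or its vicinity test, as further conflicts. The first is a minor wording difference. The second belongs to attribution, and local organ injuries would largely meet it anyway.

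**What to change.** Make 9.3.1 the single governing definition, with any grade 5 event included as in 7.1.1. Suggested wording: *a DLT is any non-hematologic toxicity of grade 4 or higher, or any grade 5 toxicity, judged possibly, probably or definitely attributable to SBRT, MWA or both, with onset no later than 30 days after MWA.*

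In 6.2.2, replace 'specifically' with 'including but not limited to'. Keep its attribution review, with vicinity stated as part of attribution, and keep its rule for patients who become ineligible for MWA. Have 6.2.2, 7.1.1, 9.4.1 and 13.5.1 refer to 9.3.1. If the investigators do intend a closed list, they should instead change 9.3.1 and 7.1.1 to match and give the reason for leaving out events such as large-bowel perforation and ureteral injury.

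The cost is a protocol wording amendment. Adverse events are already collected through the 30-day post-MWA visit, and no new tests are required; the study calendar has no liver panel, so hepatotoxicity would be found only when clinically prompted. The real downside is the lower chance of clearing all three levels shown above. Expected Phase IA size is almost unchanged and stays well within the cap of 18.
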